8.1 Informed Consent/Accent Process (in Case of a Minor or Others Unable to Consent for Themselves)	20
9 RESULT DISSEMINATION PLAN	21
10 Literature References.....	22

SUPPLEMENTS/APPENDICES

1. Exit Interview Questionnaire
2. Adult Verbal Consent Form (attached separately)
3. Outlet Flyer (attached separately)
4. Outlet enrollment questionnaire
5. Outlet consent form

ACT	Artemisinin Combination Therapy
AE	Adverse Event
AM	Antimalarial
CFR	Code of Federal Regulations
CIOMS	Council for International Organizations of Medical Sciences
CRF	Case Report Form
CHW	Community Health Worker
DFID	Department for International Development, UK
DMID	Division of Microbiology and Infectious Diseases, NIAID, NIH, DHHS
DSMB	Data and Safety Monitoring Board
FWA	Federal-Wide Assurance
GCP	Good Clinical Practice
GEE	Generalized Estimating Equation
ICF	Informed Consent Form
ICH	International Conference on Harmonisation
ID	Identification
IEC	Independent or Institutional Ethics Committee
IRB	Institutional Review Board
ISM	Independent Safety Monitor
JAMA	Journal of the American Medical Association
MOP	Manual of Procedures
N	Number (typically refers to subjects)
NEJM	New England Journal of Medicine
NIAID	National Institute of Allergy and Infectious Diseases, NIH, DHHS
NIH	National Institutes of Health
OCRA	Office of Clinical Research Affairs, DMID, NIAID, NIH, DHHS
OHRP	Office for Human Research Protections
ORA	Office of Regulatory Affairs, DMID, NIAID, NIH, DHHS
PI	Principal Investigator
PPMV	Patent and Proprietary Medicine Vendors, Nigeria
RA	Research Assistant
RD	Risk Difference
RDT	Rapid Diagnostic Test
RR	Risk Ratio
SAE	Serious Adverse Event
SMC	Safety Monitoring Committee
SOP	Standard Operating Procedure
USAID	United States Agency for International Development
WHO	World Health Organization

Title:	A randomized experiment of malaria diagnostic testing and conditional subsidies to target ACTs in the retail sector: the TESTsmART trial AIM 2
Population:	40 registered pharmacies in western Kenya, 6800 participants seeking care from these pharmacies
Number of Sites:	1
Study Duration:	24 months
Subject Duration:	30 minutes

Objectives:

The ultimate goal of a conditional subsidy scheme is to limit inappropriate use of ACTs and reduce the programmatic costs of ACT subsidies by offering them conditional upon a positive test at the point of sale.

The objective of this study is to test the effect of provider-directed and patient-directed incentives on improving the management of suspected malaria fevers that receive care in the retail sector. Provider-directed incentives include small payments for taking the time to conduct malaria-RDT testing for participants with malaria-like illness. Patient-directed incentives are inexpensive RDT testing coupled with a conditional ACT discount. The ACT discount is only applied if the RDT is positive for malaria. Outcomes will be measured by exit interviews on random days each month at each participating outlet.

Primary:

- The primary outcome will be the proportion of all ACTs that are sold to individuals with a positive malaria diagnostic test. For this outcome, a positive test is anyone who has a malaria-RDT performed at the outlet and receives a positive result or is referred from a health facility with a documented positive test result.

Secondary:

- The major secondary outcome is the proportion of suspected malaria cases that are tested. This outcome will allow us to determine whether the conditional subsidy can drive demand for testing.
- Other secondary outcomes will measure 1) adherence to the RDT result among all those tested at the outlet, 2) proportion of all suspected malaria cases that are managed appropriately (tested for malaria, and use ACT following a positive test or do not purchase an ACT after a negative test), and 3) ACT use by untested clients.

For questions regarding this protocol, contact:

Individuals: DMID Representative:

[name], MPH
Clinical Project Manager NIH/NIAID/DMID/PIPB
[name]
[contact]
[contact]

Principal Investigator: *Site investigator responsible for conducting the study:*

[name] [name]
Associate Professor of Medicine and Global Health, Duke University
[name]
[contact]
[contact]

Subcontract Principal Investigators:

[name]

Senior Manager, Malaria Commodity Access, Clinton Health Access Initiative
[name]
[contact]
[contact]
[contact]

[name]

Lecturer, Department of Medicine, Moi University School of Medicine
[name]
[contact]
[contact]
[contact]

Institutions:

Duke University

[name]
[name], Lead Grants and Contracts Administrator, DGHI
[contact]
[contact]
[contact]

1 BACKGROUND INFORMATION AND SCIENTIFIC RATIONALE

1.1 Background Information

Artemisinin combination therapies (ACTs) – the WHO-recommended first line therapy for uncomplicated malaria – have played a significant role in reducing global malaria mortality [1], but their overuse is rampant. In 2016 an estimated **216 million cases of malaria occurred worldwide, yet more than 400 million treatment courses of ACT were consumed**¹ [2]. Approximately 75% of global ACT demand is subsidized with international public funds from sources such as The Global Fund, DFID, and USAID² [3]. Overconsumption of ACTs is an unnecessary drain on scarce public health resources and threatens the future sustainability of publicly-funded subsidies. In addition, it puts both present and future patients at risk; inappropriate treatment of a non-malaria illness with an antimalarial increases case fatality rates [4, 5] and contributes to population-wide drug pressure that accelerates the spread of drug resistance [6-8].

Global over-consumption of ACTs is largely driven by its increased over-the-counter distribution in private retail outlets as a result of publicly-funded subsidies directed to the private sector [9]. In 2015, **44% of all donor-funded ACTs consumed world-wide were distributed through the private retail sector** [9] where studies have shown that between **65-91% of ACTs dispensed for malaria are actually purchased by people without malaria** [10-13]. Targeting ACTs to only those who receive a confirmatory diagnosis could dramatically reduce inappropriate ACT consumption, in alignment with WHO policy that stipulates that all febrile patients be tested before administering antimalarials.

Although more than half of families in sub-Saharan Africa seek care for febrile illness through the retail sector [14, 15], it has remained largely outside of efforts to improve rational, or diagnosis-directed, use of antimalarials. Private medicine retail outlets are made up of for-profit outlets that specialize in medicines, such as pharmacies and drug stores. These outlets are generally poorly regulated, often operate outside of formal channels, and have weak, sometimes antagonistic relationships with the formal health care sector. The lack of accountability and incentive structure undermines adherence to national case management guidelines and contributes to poor ACT stewardship in the retail sector.

Currently, recipients of Global Fund grants may use funds to subsidize RDTs in the private sector, including in private retail outlets. However, outside of a few countries (i.e., Cambodia, Ghana, Myanmar), the use of RDTs in the retail sector is uncommon as is evidenced by the very low testing rates (<10%) in the private sector in sub-Saharan Africa [2, 17]. Several studies have explored the potential role of RDTs in improving case management in the retail sector with mixed and often poor results. In most of these studies retail providers received case management training, followed by supportive supervision visits by researchers. In a few studies, the wholesale RDT price was partially or fully subsidized but retail providers were permitted to set their own price to the consumer and offer testing at their discretion [18, 19]. More often, outlets were required to provide testing free of charge or at a low fixed price. Instructions to the outlets regarding when an RDT should be performed and an ACT should be dispensed were quite rigid [20-23]. Providers were not explicitly incentivized to conduct RDTs. All of these studies shared two features – 1) ACTs were heavily subsidized for all customers and 2) there was no relationship between the RDT result and the ACT subsidy. This range of implementation strategies resulted in a wide range of testing uptake; between 7 - 100% of suspected malaria cases were tested [24]. Adherence to a negative malaria test was inconsistent (between 1-40% of those with a negative test purchased an ACT) and often a significant portion of those testing positive, up to 70%, did not take an ACT [24].

In order to align both the provider and customer incentives towards testing and targeting, the provider must be willing to perform the test and sell the appropriate medicine and, at the same time, the customer must be motivated to purchase the test and adhere to the results. We hypothesize that offering ACT subsidies for the client (conditional on a positive test), and incentives to the provider to offer malaria testing, will each, on their own, have a very modest impact on uptake of testing and targeting of ACTs in the retail sector. We further hypothesize that when combined, they will have a synergistic effect on RDT testing and ACT targeting. However, it is important to estimate the effect of each intervention separately and in combination in order to provide cogent evidence to support joint implementation. We will test the combination of subsidies for ACTs and RDTs (selected from Aim 1) paired with a provider-directed testing incentive in a four-arm cluster-

randomized controlled trial to evaluate their impact on the proportion of ACTs sold to individuals with parasitologically-confirmed malaria among those seeking care in the retail sector.

1.2 Scientific Rationale

The study will be conducted in western Kenya, where the retail sector is an important source of malaria treatment. 100% of the population is considered at risk for malaria, and the private sector is an immensely important avenue for fever management. Nationwide surveys show that 70.6% of ACTs are distributed through the private sector [25]. Given the large proportion of individuals obtaining anti-malarial drugs outside the formal sector, efforts to improve targeting of ACTs must include the retail sector.

Kenya has the programmatic goal of universal access to prompt parasitological diagnosis before treatment and has endorsed the use of malaria RDTs in the public health sector. However, very high rates of self-treatment in the retail sector undermine the explicit policy that all malaria cases should be confirmed by parasitological diagnosis. Private medicine retailers in Kenya, consisting of private pharmacies and chemists, are not routinely permitted to conduct RDTs. Instead, emphasis has been placed on shifting care to the formal health sector or deploying RDTs in the community through lay health workers. Persistently low testing rates have led Kenya to recently reconsider its position on RDT use in the retail sector, but the country has delayed any changes due to lack of rigorous data to guide policy.

Table 1: Study country characteristics

	Kenya
First line drug	AL ¹
Year adopted universal testing policy	2010
Estimated malaria cases (2016) [26]	3.5 million
Total population	50M
Percent of cases confirmed [26]	33%
Percent of fevers that seek care in retail sector	60%
Current price of ACT in retail sector (adult dose)	\$1.20
Expected price in 2018	\$1.20
Use of RDTs in retail sector?	No
Current retail cost of RDT	\$1.00 [27]
Study area	Rural
Prevalence of malaria in study area	25%

While there exist simulations of clients' decisions around testing and ACT purchasing based on prices of these commodities [25], they do not consider the motivations of providers in the retail sector to offer malaria diagnostic testing. The proposed project is a real-world implementation study that will provide insights into whether an innovative and scalable approach can help overcome the practical challenges of working through the private retail sector while improving the targeting of ACTs to individuals with confirmed malaria infection.

1.3 Potential Risks and Benefits

1.3.1 Potential Risks

The intervention proposed is an incentive to providers to perform malaria diagnostic testing and the offer of a conditionally subsidized ACT for the client in case of a positive test. The provider incentive is relatively small, so it is not likely to distort the providers' behavior to the extent where they would perform unnecessary malaria tests in order to obtain the incentive. The subsidized ACT is offered only to patients with a positive test (and only in some arms) but, the client is free to choose whether or not to use the subsidy. Participating in this study involves allowing us to record information about clients' malaria testing and treatment decisions. This includes the clients' decisions about whether to get tested for malaria using the RDT, and whether to buy an ACT. There is a small risk of breach of confidentiality of this information.

RDTs will be provided to all participating pharmacies for wholesale price. The RDTs to be used in this study are the same brand and test as those used by the Government of Kenya in public health facilities and in their community-based case management for malaria. The study will ensure availability of proper sharps disposal equipment and services to participating outlets. All clients who choose to be tested will be advised on what to do if they experience any adverse events as a result of the finger prick.

1.3.2 Known Potential Benefits

There is significant health benefit to the client in knowing their malaria infection status prior to purchasing a drug. There is also a benefit to the client to be able to purchase an effective drug at a reduced, fixed price when they have a confirmed malaria infection, which may also reduce the likelihood that they would purchase an inappropriate or outdated therapy.

In some arms, the providers get a direct monetary incentive for performing malaria diagnostic tests.

More broadly, there are important future benefits to rigorous testing of subsidy schemes that promote appropriate testing before treatment. This work will contribute to evidence-based policy making, improved access to malaria diagnosis and ultimately reduced potential for the spread of antimalarial resistance.

2 OBJECTIVES

The ultimate goal of a conditional subsidy scheme is to limit both inappropriate use of ACTs by those without a test or with a negative test, as well as to reduce the programmatic cost of ACT subsidies by offering them conditionally on a positive test at the point of sale. The objective of this study is to test the effect of provider-directed and patient-directed incentives on improving the management of suspected malaria fevers that seek care in the retail sector.

3 STUDY DESIGN

This will be a four-arm cluster-randomized trial based on an underlying 2x2 factorial design. A random sample of 40 pharmacies (clusters) will be selected from a complete sampling frame of all eligible outlets and subsequently randomly assigned in a 1:1:1:1 ratio to each of the 4 arms (see Table 2).

All clusters (Arm 1-4) will have access to RDTs at the wholesale price that enables the outlet to charge the desired retail price. The study will pre-specify the retail price so that it is consistent across all the arms and pharmacies and will work with in-country wholesalers to provide RDTs at the appropriate price to all participating outlets. In addition, all outlets will be trained on a mobile reporting app and asked to use it to record RDT and ACT sales and to facilitate payment of financial incentives. The four treatment arms are as follows:

- (1) Control (Arm 1): No price subsidy or incentive. RDTs are made available at wholesale price to the retail outlet.
- (2) Provider-directed intervention (Arm 2): Retail outlet in this arm receives a small incentive to perform an RDT for suspected malaria cases (approximately USD \$0.10 for each RDT test they report)
- (3) Client-directed conditional ACT subsidy (Arm 3): Clients visiting outlets in this arm will receive a free ACT *if* they purchase a malaria test and have a positive test result.
- (4) Combined interventions (Arm 4): Retail outlets in this arm receive an incentive to test for malaria and clients visiting these outlets receive a free ACT conditional on a malaria positive test (i.e. this arm is a combination of the provider-directed and client-directed interventions that are offered in Arm 2 and Arm 3).

Our four-arm study design will allow us to measure the effect of joint incentives to the provider and consumer, relative to no incentives and relative to either incentive alone.

Data will be collected by two independent mechanisms – provider reporting and exit interviews. First, we will examine routine reporting data submitted via mobile phones using the mobile app. All shopkeepers within each enrolled outlet will be trained to use the mobile app which reports on volume of clients, number of ACTs or other antimalarials sold, number of RDT sold. The mobile reporting app will also require the user to take a picture of every RDT test. These photos will be uploaded to the server in real-time and will be reviewed continuously by registered lab techs. This will allow the lab tech to be responsible for the diagnostic decision. Data reported through the app will primarily be used to track RDT and ACT sales in real-time and will be regularly reviewed to track proportion of positive tests, volume of RDTs used, and

visualization of a random sample of uploaded RDT photos. This routine monitoring will detect potential problems (i.e. providers who have unusually high or low test positivity rate, problems with RDT interpretation). Problems detected will trigger support supervision and/or additional on-the-job training to ensure compliance and quality of diagnosis.

Data for our main study outcomes will be collected by exit interviews with customers in order to avoid bias that may arise by relying on provider-reported data. In previous retail-sector studies, results from exit interviews and provider reports differed significantly, with exit interview results considered more reliable [22, 26]. Trained data collectors will approach customers who have transacted at the outlet and ask them if they are willing to participate in an exit interview. In our experience, refusal rates are less than 2% for these types of surveys so we expect our sample to accurately represent all transactions at the outlet. Customers will be eligible if they sought treatment for a febrile illness or malaria-like symptoms for themselves or their child, provided the child is present. Exit interviews will be conducted on randomly selected days each month and data collectors will be randomly assigned to outlets in order to minimize behavior change prompted by the presence of the interviewer. The number of days of data collection at each outlet will depend on the sales volume with a target of 10 participants per outlet per month. Customers will be asked to report whether they had a test, the results of the test, and what medicine they purchased. Basic information about household assets will also be collected in order to stratify participants on socioeconomic status.

Exit interview and provider reporting data will be compared to assess agreement between the sources. Specifically, we will compare the following indicators aggregated by outlet: the proportion tested, the proportion of tests positive and, the proportion of individuals using ACTs by test status (untested, positive or negative).

The primary outcome will be the proportion of all ACTs that are sold to individuals with a positive malaria diagnostic test. The ultimate goal of a conditional subsidy scheme is to limit both inappropriate use of ACTs by those without a test or with a negative test as well as to reduce the programmatic cost of ACT subsidies by offering them conditionally on a positive test at the point of sale. For this outcome, a positive test is anyone who is tested at the outlet and receives a positive result or is referred from a health facility with a documented positive test result. Although all ACTs purchased after a test, whether tested at the outlet or health facility, are included in the outcome measure, only ACTs purchased following a *test at the outlet* are eligible for the conditional subsidy. Our major secondary outcome is proportion of suspected malaria cases that are tested. This outcome will allow us to determine whether the conditional subsidy can drive demand for testing. Other secondary outcomes will measure 1) adherence to the RDT result among all those tested, 2) proportion of all suspected malaria cases that are managed appropriately (tested for malaria, and use ACT following a positive test and do not purchase an ACT after a negative test), and 3) ACT use by test status (untested, negative, positive).

4 Study Population

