6 STATISTICAL CONSIDERATIONS

6.1 Study Outcome Measures

The primary outcome measure is the proportion of all ACTs that are sold to individuals with a positive malaria diagnostic test defined as anyone who is tested at the outlet and receives a positive test result or is referred from a health facility with a documented positive test result.

Among secondary outcomes, behavior will be measured for individuals who were tested at the outlet. Untested clients are those who chose not to be tested and did not come with a test result from another facility. The major secondary outcome is the proportion of suspected malaria cases that are tested. This outcome will allow us to determine whether the conditional subsidy can drive demand for testing. Note that “untested people” here refers specifically to individuals that present at the shop without a referral but decline to be tested

people who were tested with an RDT

people who were tested with an RDT + # untested people who purchased an antimalarial

Other secondary outcomes will measure 1) adherence to the RDT result among all those tested at the outlet, 2) proportion of all suspected malaria cases that are managed appropriately (tested for malaria, and use ACT following a positive test or do not purchase an ACT after a negative test), and 3) ACT use by untested clients.

- Secondary outcome 2: Adherence to the RDT result among all those tested in the shop

people who tested positive and purchased ACT + # people tested negative and did not purchase any AM
people who were tested with an RDT

For those who are negative, if they buy any antimalarial (AM), including monotherapies and older therapies, they are not adhering to test result.

- Secondary outcome 3: Proportion of all suspected malaria cases that are managed appropriately in the shop

people who tested positive and purchased ACT + # people tested negative and did not purchase any AM
people who were tested with an RDT + # untested people who purchased an antimalarial

“Untested people” here refers specifically to individuals that present at the shop without a referral but decline to be tested

- Secondary outcome 4: ACT use among untested clients

people who were not tested in the shop and purchased an ACT
people who were not tested in the shop, did not have documentation of test and purchased any AM

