For the primary outcome, we include in both numerator and denominator those individuals who were referred from a health facility with a documented positive test result. That is, for the

primary outcome we are interested in evaluating the degree to which the interventions impacted the purchasing behavior of all suspected malaria cases seeking treatment. Our secondary outcomes do *not* include these individuals (i.e. the outcomes are calculated on the subset of individuals that present at the shop for testing without a referral). That is, for the secondary outcomes we are specifically interested in evaluating the degree to which the interventions impacted purchasing behavior among individuals who present at the shop for testing.

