according to the test result. We anticipate that 12% of ACTs will be purchased by clients with a positive test in the control arm (with 88% of ACTs purchased by those without a test or with a negative test). Moreover, we hypothesize that both the provider-directed intervention, and the client directed intervention on their own will only increase testing marginally (on the order of ~5 percentage points), but that among those who do test, the client-directed intervention alone will substantially increase the proportion of malaria-positive individuals who take an ACT [29]. As a result, we expect that the provider-directed intervention (Arm 2) will have only a small effect on ACT targeting, that the client-directed intervention (Arm 3) will have a somewhat larger effect, but that the largest effect will come from combining the two interventions (Arm 4) (i.e., we assume a statistical interaction). With a sample of 170 exit interviews per outlet (40 outlets in Kenya), we will have >90% power to detect a minimum difference between Arms 1 and 4 in the primary outcome of 23 percentage points. We will also have >89% power to detect a minimum difference of 16 percentage points for the main secondary comparison of interest (testing uptake).

Due to the nature of the interventions, it is not possible to blind participants and the implementation team to the allocation received. Data collectors will be blinded throughout collection and study statisticians will be blinded during the analysis phase.

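### Testing uptake counts only shop RDTs, so tests that the free ACT draws from elsewhere to the shop could be read as new demand for testing

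*Combined protocol and SAP*

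**What the plan says.** **Purpose.** The protocol summary, section 3 and section 6.1 each attach the same purpose to the major secondary outcome, the proportion of suspected malaria cases tested: "This outcome will allow us to determine whether the conditional subsidy can drive demand for testing".

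**Measure.** In section 6.1 the numerator is people tested with an RDT and the denominator is "people who were tested with an RDT + # untested people who purchased an antimalarial". The place of testing is the shop: "Among secondary outcomes, behavior will be measured for individuals who were tested at the outlet". Clients with an outside result are not counted as untested: "Untested clients are those who chose not to be tested and did not come with a test result from another facility". Of clients referred with a documented positive result the section says "Our secondary outcomes do *not* include these individuals", and it explains that "the outcomes are calculated on the subset of individuals that present at the shop for testing without a referral".

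**Incentive.** Section 3 offers the free ACT in Arms 3 and 4 only, and there "only ACTs purchased following a *test at the outlet* are eligible for the conditional subsidy".

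**Data.** The exit interview asks about a malaria test elsewhere (items 2.8 to 2.10) and a test at the shop (item 3.1). The plan defines no outcome that combines the two, and no sensitivity analysis for tests that change place.

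**The concern.** Take a client who would have been tested at a clinic or laboratory and then come to the shop to buy. Under control, this person is in neither part of the uptake ratio. If the free ACT leads the same person to skip the outside test and be tested at the shop, the person enters both numerator and denominator as a tested client. Uptake rises, although the person is tested once in either case. This is not retesting, so a stricter referral exclusion would not remove it.

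Only Arms 3 and 4 give clients this reason to move. Arm 4 v Arm 1 and Arm 4 v Arm 2 are therefore exposed. Arm 4 v Arm 3 is less so, because both arms offer the free ACT. At stake is the policy reading: a change in where people are tested could be reported as more people being tested.

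**Working it through.** **1. The plan's own figure.** Section 6.2 states more than 89% power for a 16-point difference in testing uptake. It gives no baseline uptake, no ICC for uptake and no analysable share, so the figure cannot be reproduced as a point value. With all 170 interviews per outlet, 10 outlets per arm and the primary-outcome ICC of 0.009, the effective number per arm is 1700/(1 + 169 × 0.009) = 1700/2.521 = 674. At alpha 0.05/3, power then exceeds 99% at every baseline tried from 5% to 60%. The stated figure is consistent with this only as a lower bound. The concern does not depend on it.

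**2. Direction.** Let T be shop-tested clients, B untested antimalarial buyers, O clients tested elsewhere, and x the number of O who move to the shop.

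- In-shop uptake before: T/(T + B). After: (T + x)/(T + x + B).
- Difference: xB/[(T + B)(T + x + B)], which is positive whenever x and B are positive.
- Any-location testing before: (T + O)/(T + O + B). After: (T + x + O − x)/(T + x + O − x + B). The two are identical.

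**3. Size under assumed shares.** None of these inputs is in the documents. Assume that 35% of clients without an outside test are tested in the shop, that 60% of the untested buy an antimalarial, and that half of those tested elsewhere switch. Per 100 interviewed clients:

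| Tested elsewhere | T | B | Moved | In-shop uptake before | After | False rise | Any-location, both |
|---|---|---|---|---|---|---|---|
| 5 | 33.25 | 37.05 | 2.5 | 33.25/70.30 = 47.3% | 35.75/72.80 = 49.1% | +1.8 | 38.25/75.30 = 50.8% |
| 10 | 31.5 | 35.1 | 5 | 31.5/66.6 = 47.3% | 36.5/71.6 = 51.0% | +3.7 | 41.5/76.6 = 54.2% |
| 20 | 28.0 | 31.2 | 10 | 28.0/59.2 = 47.3% | 38.0/69.2 = 54.9% | +7.6 | 48.0/79.2 = 60.6% |

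**4. A lower baseline.** Let e be the share tested elsewhere among outside-tested, shop-tested and untested-buying clients together, s the share of these who move, and u the in-shop uptake before any move. The rise is s·e·(1 − u)/[(1 − e) + s·e]. With u = 20% and s = 50%:

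- e = 5%: 0.025 × 0.8/0.975 = +2.1 points
- e = 10%: 0.05 × 0.8/0.95 = +4.2 points
- e = 20%: 0.10 × 0.8/0.90 = +8.9 points

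**5. Only the excess movement counts.** RDTs are sold at one price in all arms, so some tests may move in Arms 1 and 2 as well. Take e = 10% and u = 20%, with a quarter moving in Arm 1 and half in Arm 4. Uptake is (18 + 2.5)/(90 + 2.5) = 22.2% against (18 + 5)/(90 + 5) = 24.2%, a false difference of 2.0 points instead of 4.2. With equal movement in both arms it is zero.

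**6. If outside-tested clients are counted as untested.** Section 6.1 also describes the untested as people without a referral who decline a test, which could take in some clients with an outside result. If all 10 outside-tested clients in step 4 bought an antimalarial and counted as untested, uptake would be 18/100 = 18.0%, and 23/100 = 23.0% after half moved. The direction is the same.

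**The case against.** **The restriction is deliberate.** Section 6.1 says that the secondary outcomes concern people who present at the shop for testing, and the trial is about the retail sector. On that reading, demand means demand at the shop. This stands for a claim about in-shop testing. It does not carry the broader statement about demand, and the subsidy can itself change, after randomisation, who belongs to that subset.

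**A reader might infer that the uptake contrasts are inflated.** The documents do not show this. The bias needs clients to know of the free ACT before they go elsewhere. An outlet flyer is listed among the supplements, but its content is not available here. Movement that occurs in all arms cancels (step 5).

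**A reader might infer that relocation could account for the effect the plan expects.** Section 6.2 says that each intervention alone "will only increase testing marginally (on the order of ~5 percentage points", and the assumed false rises are of that order. But that figure is for single interventions. The exposed contrasts are Arm 4 v Arm 1 and Arm 4 v Arm 2, and a single intervention against control is not among the plan's three comparisons. For testing uptake, section 6.2 names a difference of 16 points.

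**A reader might infer that every outside-tested client drops out of the ratio.** The explicit exclusion names only documented positives. Outside negatives and undocumented results are covered only by the definition of untested, which section 6.1 words in two ways. Hence largely, not wholly, left out.

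**A reader might extend the point to the primary outcome.** A documented outside positive counts there wherever the test was done, so that outcome is less exposed.

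**Conclusion.** The concern holds in a conditional form. Given the definition in section 6.1 and the shop-test condition in section 3, every test that moves to the shop raises measured uptake without adding a tested person. The Arm 4 v Arm 1 and Arm 4 v Arm 2 differences could be inflated to the extent that the free ACT causes more such movement than occurs in Arms 1 and 2.

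The size is unknown. With 5% to 20% tested elsewhere, half of them switching and no movement in the comparison arm, the false rise is about 2 to 8 points at a control uptake of 47.3%, and 2.1 to 8.9 points at 20%. Any movement in the comparison arm reduces it. All these shares are assumptions. The outcome supports a statement about in-shop testing; on its own it does not support one about demand for testing overall.

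**What to change.** 1. In section 6.1, label the current outcome in-shop testing uptake.
2. Add any-location testing uptake. Numerator: clients tested in the shop (item 3.1 = Yes) or elsewhere (item 2.8 = 1 or 2). Denominator: those clients plus clients with no test anywhere who bought an antimalarial. Count each client once, and use the same model and contrasts. With matching denominators, the two outcomes differ only in how outside tests are handled.
3. State the coding. Item 2.8 is skipped when item 2.5 is No or Don't know, and item 2.8 has its own Don't know code, so both need a rule.
4. Report the share tested elsewhere by arm.
5. In the protocol summary, section 3 and section 6.1, base the statement on demand for testing on the any-location estimate and its confidence interval, read alongside in-shop uptake. Do not treat a non-significant any-location rise as proof of relocation.

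The cost is SAP wording and one derived outcome from items already on the form. State two limitations: outside tests are partly self-reported (item 2.9 separates observed reports from self-report), and clients who would have been tested and treated wholly at a clinic remain unseen, so relocation of their tests would still look like new testing. Both ratios also move if fewer untested clients buy an antimalarial.
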